11.4 Quality control

As in our prior studies, health interviewers will be trained by a senior coordinator and certified by [name] in each component of data collection, using a detailed checklist developed for this trial. Health interviewers are rigorously evaluated for adherence to protocol, prior to beginning data collection and every six months after initial certification.

12.0 Provisions to Monitor the Data to Ensure the Safety of Subjects

Serious adverse events will be reported to the DSMB within seven days of each serious adverse event. Adverse event data will be reported to the DSMB every six months during the study, and/or as requested by the DSMB. The DSMB will have the ability to stop the study at any time if there are concerns about safety.

13.0 Withdrawal of Subjects*

Subjects may withdraw from the research at any time. If they decide to leave the research, they should contact the investigator, [name].

If they stop being in the research, already collected data may not be removed from the study database. They will be asked whether the investigator can collect data from their routine medical care. If the subject agrees, this data will be handled the same as research data.

Subjects who withdraw from the study will be replaced by another PAD participant(s) who meets eligibility criteria. The newly enrolled PAD participants will begin the study at the dose at which the withdrawn participant would have received next, if they had not withdrawn.

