Specific Aim. Because subcutaneously administered unacylated ghrelin has not been studied in humans, we will establish the association of increasing doses of subcutaneous unacylated ghrelin with circulating levels of unacylated ghrelin and brachial artery flow-mediated dilation (FMD) and levels of circulating inflammatory biomarkers. To achieve this aim, six PAD participants age 55 and older will receive a single subcutaneous injection of unacylated ghrelin at doses of 10 ug/kg, 20 ug/kg, and 40 ug/kg, respectively, on three separate days at least one week apart. Unacylated ghrelin levels will be measured at baseline and at defined intervals after each subcutaneous injection (30 minutes, 60 minutes, 1.5 hours, 3 hours, 6 hours, 8 to 12 hours and 24 hours). Brachial artery FMD will be measured at baseline, before the unacylated ghrelin injection, approximately six to eight hours, and 24 hours after each unacylated ghrelin injection (8). Circulating levels of inflammatory biomarkers will be measured at baseline and at six hours, 8-12 hours, and 24 hours after the subcutaneous injection of unacylated ghrelin. The lowest dose of subcutaneously delivered unacylated ghrelin that maximizes brachial artery FMD, maximizes levels of unacylated ghrelin, and minimizes circulating levels of inflammatory biomarkers will be used in future study.

PROTOCOL TITLE: Unacylated Ghrelin to Improve Functioning in PAD: the GIFT Trial

Specific Aim 2. We will assess the safety of increasing doses of unacylated ghrelin in six patients with PAD age 55 and older.

1.2 *Hypotheses.*

We hypothesize that unacylated ghrelin, administered subcutaneously, will increase brachial artery flow-mediated dilation (FMD) and reduce circulating levels of inflammatory biomarkers and that higher doses of subcutaneously administered unacylated ghrelin will be associated with greater increases in brachial artery FMD and lower circulating levels of inflammatory biomarkers.

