3.0 Inclusion and Exclusion Criteria

3.1 Screening for eligibility.

Recruitment. We will identify six PAD participants age 55 and older meeting eligibility criteria for our proposed pilot study. For this pilot study, we will contact six PAD patients who participated in our previous research studies and agreed to be contacted for future research studies conducted by [name].

PROTOCOL TITLE: Unacylated Ghrelin to Improve Functioning in PAD: the GIFT Trial

We may also use the Enterprise Data Warehouse to identify six consecutive patients with PAD to participate in this pilot study.

3.2 Criteria.

Inclusion Criteria. All participants will be age 55 and older. All will have an $ABI \leq 0.90$ at baseline. $ABI \leq 0.90$ is a well-accepted standard for defining PAD (44-47). In addition, people with a history of lower extremity revascularization for PAD will be eligible.

Exclusion Criteria.

1. Above or below-knee amputation, critical limb ischemia, and wheelchair confinement.
2. Cardiovascular event during the previous three months. [Note: Participants who have undergone coronary revascularization for a cardiac event during the previous three months may still qualify.]
3. Major medical illnesses including renal disease requiring dialysis, or cancer requiring treatment in the previous year.
4. Participation in another clinical trial or completion of a clinical trial in the previous month, unless they were in the control group of the previous trial.
5. Unwilling to attend nine study visits over approximately six months.
6. Surgery including lower extremity revascularization or orthopedic surgery in the previous month or anticipated surgery in the next three months.
7. Greater than 15 mmHg difference in blood pressure in both arm pressure measurements during the ABI, diagnosis of Raynaud's phenomenon, or unable to have the blood pressure checked in both arms.
8. Blood pressure $< 90/50$ at baseline.
9. Non-English speaking, a visual impairment that limits ability to read the consent, or a hearing impairment that interferes with study participation.
10. In addition to the above criteria, investigator discretion will be used to determine if the trial is unsafe or not a good fit for the potential participant.

3.3 Special Populations.

Vulnerable populations (fetuses, pregnant women, children, prisoners, and institutionalized persons) and adults unable to consent will not be included in this study.

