We will test doses of 10 ug/kg, 20 ug/kg, and 40 ug/kg of unacylated ghrelin on three separate days for each participant. These doses were selected based on published literature and the experience of our consultants [name], who has an ongoing study of intravenously administered unacylated ghrelin in healthy people (R01-DK097550) and [name], who has an ongoing study of subcutaneously administered acylated ghrelin in older frail people without PAD (R21-AG040488).

Justification for proposed doses of unacylated ghrelin. Unacylated ghrelin is a synthetic 28 amino-acid protein. The ½ life of intravenously administered unacylated ghrelin is 30-34 minutes, which is comparable to but slightly longer than the ½ life of insulin and glucagon (9). In comparison, the ½ life of intravenously administered acylated ghrelin is 9 to 11 minutes (9). A portion of intravenously administered acylated ghrelin is converted to unacylated ghrelin (9). In contrast, unacylated ghrelin is not converted to acylated ghrelin (9). In healthy people, circulating levels of unacylated ghrelin are higher than those of acylated ghrelin, in a ratio that is typically 4:1 but ranges from 2:1 to 9:1 (9,11,48). In a study of healthy people, a 4X higher dose of intravenously administered unacylated ghrelin achieved a CMax that was twelve times higher than that for intravenously administered acylated ghrelin (9). Because of the longer ½ life of unacylated ghrelin and the substantially greater CMax achieved with unacylated ghrelin as compared to acylated ghrelin, we will begin with a subcutaneous unacylated ghrelin (10 ug/kg) dose that is comparable to that selected by [name] for her study of subcutaneously administered acylated ghrelin. Next, we will test a subcutaneous dose of unacylated ghrelin that is 2X the starting dose (20 ug/kg). Finally, we will test a subcutaneous dose of unacylated ghrelin that is 4X times the starting dose (40 ug/kg). Four times the starting dose was selected as the maximal dose to test because circulating levels of unacylated ghrelin are approximately four times higher than circulating levels of acylated ghrelin and because of the higher CMax of unacylated as compared to acylated ghrelin (9,11,48). Although the GIFT Trial will administer unacylated ghrelin subcutaneously, we anticipate that, similar to intravenous administration, the maximum concentration of unacylated ghrelin will be greater than that for acylated ghrelin.

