9.0 Procedures Involved

9.1 Study design.

STUDY OVERVIEW. We will identify the lowest subcutaneous dose of unacylated ghrelin that maximizes brachial artery flow mediated dilation (FMD). These PAD participants will receive three different subcutaneous doses of unacylated ghrelin on three different days and will undergo measurement of unacylated ghrelin levels prior to the injection and at specified time intervals. Each dose will be separated by a wash-out period of \geq one week. Data will be obtained for all six participants at each dose before moving to the next dose. We will test doses of 10 ug/kg, 20 ug/kg, and 40 ug/kg of unacylated ghrelin on three separate days for each participant. These doses were selected based on published literature and the experience of our consultants [name], who has an ongoing study of intravenously administered unacylated ghrelin in healthy

PROTOCOL TITLE: Unacylated Ghrelin to Improve Functioning in PAD: the GIFT Trial

people (R01-DK097550) and [name], who has an ongoing study of subcutaneously administered acylated ghrelin in older frail people without PAD (R21-AG040488).

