Selecting the dose of unacylated ghrelin for future study. We will select the lowest subcutaneous dose of unacylated ghrelin that maximizes brachial artery FMD and minimizes circulating levels of oxidative stress. We will also use unacylated ghrelin levels to select the unacylated ghrelin dose. In selecting the dose, greater increases in brachial artery FMD and lower levels of oxidative stress will be prioritized over the level of unacylated ghrelin. For example, if the dose of 40 ug/kg results in substantially higher levels of unacylated ghrelin compared to the dose of 20 ug/kg, but improvement in brachial artery FMD is similar between the 20 ug/kg and the 40 ug/kg doses, then we will select a dose of 20 ug/kg for use in a possible future trial of unacylated ghrelin in PAD patients.

PROTOCOL TITLE: Unacylated Ghrelin to Improve Functioning in PAD: the GIFT Trial

9.2 Describe all research procedures.

Please see sections 7.0, 8.1, 8.2, and 9.1 above.

Ankle Brachial Index (ABI). After the participant rests supine for five minutes, the right brachial, dorsalis pedis (DP), posterior tibial (PT) and left DP, PT, and brachial artery pressures are measured using a hand-held Doppler probe. Pressures are measured twice. The ABI is calculated for each leg by dividing the average of the DP and PT pressures by the average brachial pressure.

Questionnaire Administration. Participants will be administered study questionnaires by a trained and certified health interviewer.

Brachial Artery Flow-Mediated Dilatation (FMD). Brachial artery imaging will be performed by a Registered Diagnostic Cardiac Sonographer according to established protocol (44,45). Changes in FMD will be read by [name] University of Wisconsin Atherosclerosis Imaging Research Program Core Laboratory by a single reader blinded to participant characteristics. We have more than a decade of experience working with [name] reading center (44,47,48). Measurement reproducibility in [name] laboratory has a median FMD difference of 0.02% (inter-quartile range: -0.03 to 0.04).

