11.0 Data and Specimen Management

11.1 Data management.

Data is recorded using preprogrammed instruments and an electronic case report form using secure, HIPAA-compliant REDCap database software on servers maintained by Northwestern's Clinical and Translational Sciences Institute. We have substantial experience with REDCap.

Data Safety Monitoring Board (DSMB). We have identified three nationally recognized experts to serve on the DSMB.

Power Estimates. The primary aim of the GIFT Trial is to obtain preliminary data that will allow us to determine whether there is sufficient 'signal' from unacylated ghrelin to warrant additional study of unacylated ghrelin in older patients with PAD. In addition, the GIFT Trial will allow us to obtain an estimate of effect size and standard deviation of change in our study outcomes when unacylated ghrelin is administered to older PAD participants. Finally, the GIFT Trial will allow us to determine the feasibility of administering unacylated ghrelin to older patients with PAD. Because this is a preliminary study, no power calculations were performed.

Statistical Analyses. Simple statistics will be performed to assess changes in brachial artery FMD over time in response to each unacylated ghrelin injection. Simple statistics will also be performed to analyze changes in levels of unacylated ghrelin and acylated ghrelin and circulating levels of oxidative stress after each subcutaneous injection of unacylated ghrelin.

11.2 Power analysis.

A power analysis is not applicable, given the exploratory nature of this research.

11.3 Steps to secure data to maintain confidentiality during storage, use, and transmission.

First, all research assistants must complete training in protection of subject privacy and prevention of disclosure of identifying information.

PROTOCOL TITLE: Unacylated Ghrelin to Improve Functioning in PAD: the GIFT Trial

Second, all data collection forms are maintained in a secure office space.

Third, our study databases are maintained in locked computer files or on secure hard-drives that are password protected; to which only authorized staff have access. [name] or a study manager must provide permission for programmers and research assistants to access study databases.

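### The replacement rule in section 13.0 leaves an injected but unmeasured dose at five FMD changes, and after a between-dose withdrawal leaves five complete three-dose series instead of six

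*Combined protocol and SAP*

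**What the plan says.** Section 1.1 (Specific Aim) describes a within-person design: six participants "will receive a single subcutaneous injection of unacylated ghrelin at doses of 10 ug/kg, 20 ug/kg, and 40 ug/kg, respectively, on three separate days". Section 7.0 repeats it: "We will test doses of 10 ug/kg, 20 ug/kg, and 40 ug/kg of unacylated ghrelin on three separate days for each participant". Section 9.1 adds a condition for escalation: "Data will be obtained for all six participants at each dose before moving to the next dose". Section 7.0 states the same plan.

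For withdrawals, section 13.0 says that the person "will be replaced by another PAD participant(s) who meets eligibility criteria", and then: "The newly enrolled PAD participants will begin the study at the dose at which the withdrawn participant would have received next". It does not provide for a dose that was injected but not measured. It also does not say what happens after a withdrawal during the 40 ug/kg period, when no next dose exists.

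Section 9.1 chooses the future dose by comparing doses. It ranks FMD gains and oxidative stress above ghrelin level, and its worked example is the case where "improvement in brachial artery FMD is similar between the 20 ug/kg and the 40 ug/kg doses". The analysis in section 11.1 is brief: "Simple statistics will be performed to assess changes in brachial artery FMD over time in response to each unacylated ghrelin injection". No paired or mixed-model comparison of doses is named.

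**The concern.** The study's product is a dose for later trials, and that choice compares FMD change between doses in very few people. The three-dose series lets each person act as his or her own control. A newcomer who enters at 20 or 40 ug/kg never supplies the lower dose, so that series cannot be restored. Withdrawal causes the loss, but the entry dose is what prevents the replacement from making it good.

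Separately, two operative rules can contradict each other. Section 9.1 asks for six people's data before escalation, while section 13.0 can send a replacement past a dose that has only five FMD changes.

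**Working it through.** **Inputs.** Six participants, three doses, the all-six condition (sections 7.0 and 9.1) and the entry rule (section 13.0). There is no power or precision figure to reproduce, because section 11 says that none was calculated. The documents give no SD of FMD change, no within-person correlation and no withdrawal rate. The correlation (rho) and the withdrawal rates below are therefore assumptions, shown over a range.

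**Step 1: counts after one withdrawal, with section 13.0 read literally.** Five people complete everything. The withdrawn person and the replacement are added to them.

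| Withdrawal | FMD changes at 10/20/40 | Complete series | Pairs 10v20 / 20v40 / 10v40 |
|---|---|---|---|
| Before any injection | 6/6/6 | 6 | 6/6/6 |
| Injected at 10, no FMD | 5/6/6 | 5 | 5/6/5 |
| After FMD at 10 | 6/6/6 | 5 | 5/6/5 |
| Injected at 20, no FMD | 6/5/6 | 5 | 5/5/5 |
| After FMD at 20 | 6/6/6 | 5 | 6/5/5 |
| Injected at 40, no FMD | 6/6/5 | 5 | 6/5/5 (no next dose defined) |

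The three rows without an FMD fall short of six at one dose. The two between-dose rows keep six per dose but lose a complete series. In each of those two rows, one contrast keeps all six pairs.

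**Step 2: paired interval.** The 95% half-width, in SDs of the paired difference, is t(0.975, k-1)/√k.
- k = 6: 2.571/√6 = 1.049
- k = 5: 2.776/√5 = 1.242
- Ratio: 1.242/1.049 = 1.18, or 18% wider. The standard error alone rises by √(6/5) = 1.095.

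**Step 3: six-slot means.** Suppose instead that the withdrawn person and the replacement share one slot and the two dose means are subtracted. Let s be the SD of FMD change.
- Six pairs: variance 2s²(1-rho)/6 = 12s²(1-rho)/36.
- Five pairs plus one slot filled by two people: [5·2s²(1-rho) + 2s²]/36 = s²[10(1-rho) + 2]/36.
- SE ratio: √{[10(1-rho) + 2]/[12(1-rho)]}. At rho = 0 it is √(12/12) = 1.00, at 0.5 √(7/6) = 1.08, and at 0.8 √(4/2.4) = 1.29.

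**Step 4: participant-effect model.** This is generalised least squares over all three doses, with equal within-person correlations treated as known. For a contrast that spans the replacement after a between-dose withdrawal, the SE ratio is 1.00, 1.04 and 1.06 at rho 0, 0.5 and 0.8. The contrast that does not span it has ratio 1.00.

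**Step 5: how often.** If each of six people has an assumed chance w of leaving after the first or second dose, the chance that at least one does is 1-(1-w)^6. This gives 27%, 47% and 74% at w = 5%, 10% and 20%. These figures cover any such withdrawal. They are not the chance of an injected but unmeasured dose, which is smaller.

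**The case against.** The strongest defence is that section 11.1 plans a summary of change after each injection, and each injection has its own pre-injection FMD. For a withdrawal between doses, section 13.0 delivers what the escalation condition asks for, which is six people at each dose. That is a coherent choice for an exploratory pilot. It also spares the newcomer long visits and extra exposure to a drug not previously given subcutaneously to humans, with no direct benefit. All of this stands. What remains is that the dose is chosen by comparing doses, and section 13.0 is silent on how to do so after a replacement.

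The conflict with the escalation condition is also narrow. FMD is due at 6 or 8-12 hours, and participants are watched on site for about 8-12 hours (section 9.3). The condition could be read as requiring a missing reading to be made up, but section 13.0 gives no means of doing that.

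Saving visits is a weaker defence. Replacements must meet the eligibility criteria, which exclude anyone "Unwilling to attend nine study visits over approximately six months". They have therefore accepted nine visits, although accepting them does not remove the burden.

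A reader might infer that any replacement makes paired and unpaired comparisons disagree. The counts do not support this. After a withdrawal following the FMD at 10 ug/kg, all six 20v40 pairs survive, and that is the contrast in section 9.1's example. A reader might also infer interval losses of about half. With four pairs the half-width is 3.182/√4 = 1.591, which is 52% wider than with six. That needs two withdrawals at different stages in different slots, and it affects only 10v40.

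**Conclusion.** The concern holds in a limited form. Read literally, section 13.0 conflicts with sections 7.0 and 9.1 when a dose has been injected but its FMD not obtained: that dose keeps five changes. This is probably uncommon. After a between-dose withdrawal, readings per dose stay at six and complete series fall to five. The contrasts that span the replacement lose precision: the paired interval is about 18% wider, or the standard error is 0-29% larger with six-slot means, or 0-6% larger with a participant-effect model. The last two ranges rest on assumed rho between 0 and 0.8, and the model figure treats rho as known.

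The documents do not support a claim of bias. The effect is added noise unless newcomers differ systematically from those who left. Nothing is lost if no one withdraws, or if the withdrawal precedes the first injection. The change is worth making because it is small and specific, not because the trial fails without it.

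**What to change.** **Minimum.** Amend section 13.0 so that a replacement starts at the earliest dose for which the withdrawn participant has no post-injection FMD, and state which reading counts (6 or 8-12 hours, or 24 hours as well). This makes sections 13.0 and 9.1 consistent and covers a withdrawal during the 40 ug/kg period. It costs one repeated injection when a dose went unmeasured, and nothing otherwise. It does not restore the sixth series unless the unmeasured dose is 10 ug/kg, so show the number of pairs beside each contrast.

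**Preferred.** Start every replacement at 10 ug/kg and give all three doses in order, at least one week apart. Compare FMD between doses in the six people with all three doses, and keep the withdrawn person's data in the per-dose and safety summaries. Per-dose counts can then be 7/6/6 or 7/7/6, so state in advance that the six complete series supply the dose contrast. Newcomers also get the same step-up as the others.

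**Cost of the preferred change.**
- For a single between-dose withdrawal, one extra injection (after 10) or two (after 20): 19 or 20 in total instead of 18.
- Three extra visits per added dose, one of them lasting 8-12 hours.
- A finish at least one to two weeks later. The other five may be held back: by about a week before 40 ug/kg after a withdrawal at 10, and by the newcomer's 10 and 20 ug/kg steps if the 20 ug/kg dose went unmeasured.
- A full course needs at least 7 + 7 + 1 = 15 days from first injection to last 24-hour visit. That is within the six months per participant, and within the month between the 12-month enrolment and 13-month data-collection targets. It is a best case, and recruiting the replacement takes further time.

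Neither change removes selection through withdrawal, and a replacement may also leave.

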Minimizing risks related to unacylated ghrelin. The six participants who receive the three injections of increasing doses of unacylated ghrelin will be observed at Northwestern Medical Center for approximately 8-12 hours after each injection. Participants will be observed for side effects. Participants will also return at 24-hour follow-up for assessment. The three injections will be separated by intervals

PROTOCOL TITLE: Unacylated Ghrelin to Improve Functioning in PAD: the GIFT Trial

of at least one week. Safety will also be monitored by our data safety monitoring board (DSMB) (see below).

Minimizing risk related to baseline and follow-up testing. All study coordinators undergo baseline training and are certified by [name] before beginning data collection. Training and certification involves ensuring that coordinators are trained in methods to help minimize falls. [name] re-certifies coordinators every six months to ensure continued adherence to study protocol. Those who are not adhering to protocol undergo additional training followed by re-certification.

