14.0 Risks to Subjects*

Overview of the GIFT Trial and anticipated characteristics of study participants. Six participants with PAD age 55 and older will participate in a

PROTOCOL TITLE: Unacylated Ghrelin to Improve Functioning in PAD: the GIFT Trial

dose finding study, in which participants will receive three different doses of unacylated ghrelin (10 ug/kg, 20 ug/kg, and 40 ug/kg) on three different days. Each dose will be separated by at least one week. Based on our previous work involving older participants with PAD, we anticipate that the average age will be approximately 76 years, that at least 33% of participants will be minorities, and that approximately 50% will be women. For example, in our recently completed SILC randomized controlled clinical trial of exercise in patients with PAD participants included 52% women and 45% African-Americans (39). In general, older patients with PAD have a high prevalence of comorbid diseases, particularly coronary artery disease, cerebrovascular disease, diabetes mellitus, and pulmonary disease. Thus the patient population is likely to be of generally poorer health than that of older men and women without PAD in the general population. Inclusion and exclusion criteria are provided in section 3.2.

Sources of material. We will collect data on levels of circulating unacylated ghrelin at multiple defined time points within a 24-hour period after three increasing doses of subcutaneously injected unacylated ghrelin. We will also measure brachial artery flow-mediated dilation (FMD) at baseline and at six or 8-12 hours after each of the three doses of subcutaneously injected unacylated ghrelin. Information obtained from the levels of circulating unacylated ghrelin and the brachial artery FMD will be used to select the dose of subcutaneous unacylated ghrelin to use in future trials.

Potential Risks.

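### The replacement rule in section 13.0 allows a first exposure at 20 or 40 ug/kg, which conflicts with sections 7.0, 9.1, 9.3 and 14.0, and by-dose safety results would pool these entrants with people already exposed to lower doses

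*Combined protocol and SAP*

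**What the plan says.** Section 13.0 (Withdrawal of Subjects) provides that "Subjects who withdraw from the study will be replaced by another PAD participant(s) who meets eligibility criteria". It adds that these newcomers "will begin the study at the dose at which the withdrawn participant would have received next". It sets no limit on the timing, number or reason of withdrawals that lead to replacement.

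Other sections describe the course of treatment without a replacement case:

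- Section 9.1, repeating section 7.0: "We will test doses of 10 ug/kg, 20 ug/kg, and 40 ug/kg of unacylated ghrelin on three separate days for each participant".
- Section 9.3, on minimizing risks from the drug: "The six participants who receive the three injections of increasing doses of unacylated ghrelin will be observed at Northwestern Medical Center".
- Section 14.0, in its overview: "participants will receive three different doses of unacylated ghrelin (10 ug/kg, 20 ug/kg, and 40 ug/kg) on three different days". Its paragraph on sources of material refers to measurements taken "after three increasing doses of subcutaneously injected unacylated ghrelin".

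Sections 7.0 and 9.1 also state an escalation rule for the group: data on all six participants at one dose come before the next dose. Section 1.1 says that the drug has not been given subcutaneously to humans before and has not been studied in PAD. Its Specific Aim 2 is safety across increasing doses in six patients.

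**The concern.** A reader of sections 7.0, 9.1, 9.3 and 14.0 would conclude that anyone injected with 20 ug/kg has already had 10, and that anyone injected with 40 has already had 10 and 20. Section 13.0 allows otherwise. Two things are at stake.

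First, the protocol gives two accounts of what a participant receives, for a route with no earlier human use, and the available risk text covers only one of them.

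Second, Specific Aim 2 rests on about six people per dose. A reaction at 40 ug/kg in someone who has never had the drug is different information from a reaction in someone already given 10 and 20. Section 11.1 promises only simple statistics, describes none for safety, and does not say how people with one or two doses are handled. As written, the two kinds of exposure would be pooled without a label.

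**Working it through.** The documents give no power, dropout or error-rate figure for this point, so there is no stated number to reproduce. The check applies section 13.0 to the dose sequence and compares the result with the other sections.

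**Step 1. What a replacement receives.** Inputs: the sequence 10, 20, 40 ug/kg (section 7.0) and the entry rule (section 13.0). Multiple = first dose / 10.

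| Withdrawn after | Replacement receives | First exposure | Multiple of starting dose |
|---|---|---|---|
| 0 doses | 10, 20, 40 | 10 | 10/10 = 1 |
| 1 dose | 20, 40 | 20 | 20/10 = 2 |
| 2 doses | 40 | 40 | 40/10 = 4 |
| 3 doses | none left | – | – |

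Only the first row agrees with the three-dose description in sections 7.0, 9.1, 9.3 and 14.0. Rows two and three contradict it.

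**Step 2. Which safeguards reach a replacement.** Section 9.3 lists four measures specific to the drug.

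- Observation for about 8 to 12 hours following every injection: applies.
- The next-day check ("Participants will also return at 24-hour follow-up for assessment"): applies.
- At least one week between injections: applies between 20 and 40 ug/kg, and has no role for someone who gets one dose.
- DSMB monitoring: applies.

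The group-level escalation in sections 7.0 and 9.1 also remains, because the lower dose has been given to the rest of the group first. What a later entrant lacks is a lower dose in the same person. Section 9.3 mentions the rising sequence when it identifies who is observed, but does not list it as a protective measure.

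**Step 3. Share of the by-dose safety data.** With six people per dose, one replacement is 1/6 = 17% of that dose's data, and two are 2/6 = 33%. This assumes that the withdrawn person contributes nothing at that dose. At 20 ug/kg the first exposures are those who enter there. At 40 ug/kg they are those who enter at 40, while someone who entered at 20 has had one earlier dose instead of two.

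**Step 4. Side effect on the dose comparison.** Let m people be replaced after their first or second dose; m is an assumption. Those with both 10 and 40 ug/kg number n = 6 − m, and those ever exposed number 6 + m. The 95% half-width for a paired 10 versus 40 difference, in SDs of that difference, is t(0.975, n−1)/√n:

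| m | n | Ever exposed | Half-width |
|---|---|---|---|
| 0 | 6 | 6 | 1.05 |
| 1 | 5 | 7 | 1.24 |
| 2 | 4 | 8 | 1.59 |
| 3 | 3 | 9 | 2.48 |

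The withdrawal itself causes the loss of pairs. The entry rule means that the replacement does not restore them. Six people at each dose therefore need not be the same six.

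**Step 5. What the DSMB would know.** Under section 12.0, serious events reach the board within seven days; other adverse event data go every six months or on request. Section 9.3 speaks more generally of timely reporting under pre-specified requirements. Doses may be one week apart. Nothing in the available text ensures that the board is told before a new person enters at 20 or 40 ug/kg.

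**The case against.** The strongest reply is that sections 7.0, 9.1 and 14.0 give the planned course, while section 13.0 is an open, specific exception. Read together, they leave no doubt about which dose a replacement gets, and a cross-reference would settle it. The section 14.0 statement comes from an overview and is not a risk-control claim. The DSMB is to approve the protocol before data collection and can stop the study at any time. With so few people, prior exposure can be worked out from participant and visit.

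Much of this stands. The dose a replacement would get is not ambiguous, and oversight exists. But sections 7.0 and 9.1 speak of each participant without qualification, and section 9.3 describes the whole group of six in the same way. That prior exposure can be worked out does not mean that a by-dose table will show it.

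A reader might infer that the stated risk protections fail for replacements. The documents do not support that: the measures in section 9.3 and the group escalation still reach them, and no available section names a lower first dose in the same person as a protection. Text under the Potential Risks heading in section 14.0 was not available for this check, so a statement there cannot be ruled out. A reader might also infer that the person replaced left because of a reaction. Section 13.0 gives no reasons for withdrawal, so that would be speculation.

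**Conclusion.** The point holds as a contradiction in the text with a modest analytic consequence. Section 13.0 permits a first exposure at 2 or 4 times the starting dose, while four other sections describe a full three-dose course with no exception. The available risk text is silent on later entry. By-dose safety at 20 and 40 ug/kg would pool first exposures with repeat exposures, at about one sixth of the data per replacement, assuming six people per dose.

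How likely this is cannot be stated. The documents give no dropout rate, and any probability would depend on an assumed rate and on whether it is counted per person or per gap between doses. If nobody withdraws between doses, the issue does not arise. The case for change rests on the low cost of the remedy, and no view is taken on which entry dose is right.

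**What to change.** Reconcile section 13.0 with sections 7.0, 9.1, 9.3 and 14.0 so that the design text, the risk text and the replacement rule agree. The choice of rule belongs to the investigators and the DSMB. If entry above the first dose remains possible, the risk text should say so.

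Whichever rule is kept:

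- record for every injection which earlier doses that person has had;
- show replacements separately in by-dose safety results, and state in section 11.1 how people with fewer than three doses enter the dose comparison;
- inform the DSMB when an entry above the first dose is planned.

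The cost is some protocol wording, one column in the safety listing and a short notice to the DSMB. No extra participants, visits or measurements are needed.
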